## 5 INVESTIGATIONAL PLAN

### 5.1 Study Design

This is an open label, single arm, phase 2 study of men with neuroendocrine phenotype prostate cancer to assess the safety and efficacy of avelumab 10 mg/kg IV every 2 weeks until progression or intolerable side effects. Cycles will be 4 weeks long and thus include 2 doses of avelumab. This study will be at multiple centers with the Duke Cancer Institute as the lead site. For stage 1, Duke will serve as the single site for this study. For stage 2, the study would be expanded to include additional sites

through the Department of Defense Prostate Cancer Clinical Trials Consortium (DOD PCCTC). All subjects will be followed for disease progression and death from the date that the subjects were registered to the protocol.

At radiologic progression a standard of care post-treatment progression biopsy will be collected at the discretion of the treating provider, and if proper consent is obtained, additional tissue will be collected for research tests including assessments of resistance mechanisms and immune checkpoint status. The additional research tissue will be banked in the Biospecimen Repository & Processing Core (BRPC) under Pro00080869. The study team will also pursue dual consent to BRPC Pro00035974 for future unspecified research.

Men will continue on their ADT used at entry into study per investigator with subsequent changes made per investigator. Men not on ADT at time of entry due to being purely SCPC can remain off ADT. Men with SCPC on ADT at study entry can remain on ADT per investigator while all men with mixed histologies should remain on active ADT during trial participation.

Men will be allowed to receive palliative radiation to any disease site indicated by the treating physician at any time before or during the study, provided that another untreated site of measureable disease is present at baseline.

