## 5.2 Drug Discontinuation Criteria

All subjects will be monitored for adverse events (AEs) on treatment using NCI CTCAE v4.0 or the most current version. Stopping rules based on unacceptable toxicities will be used in this study. Avelumab will be discontinued in the patient if there is unacceptable toxicity defined as:

- Any grade 5 treatment-related death
- Any Grade 4 AE except for single laboratory values out of normal range that are unlikely related to study treatment as assessed by the Investigator, do not have any clinical correlate, and resolve within 7 days with adequate medical management
- Any Grade 3 AE except for any of the following:
  - Transient ( $\leq 6$  hours) Grade 3 flu-like symptoms or fever, which is controlled with medical management
  - Transient ( $\leq 24$  hours) Grade 3 fatigue, local reactions, headache, nausea, emesis that resolves to Grade  $\leq 1$
  - Single laboratory values out of normal range (excluding Grade  $\geq 3$  liver function test increase) that are unlikely related to study treatment according to the Investigator, do not have any clinical correlate, and resolve to Grade  $\leq 1$  or baseline within 7 days or by the next visit with adequate medical management
  - Tumor flare phenomenon defined as local pain, irritation, or rash localized at sites of known or suspected tumor
  - Change in Karnofsky Performance Status to  $\leq 40$  that does not resolve to  $\geq 50$  within 14 days (infusions should not be given on the following cycle, if the Karnofsky Performance Status is  $\leq 40$  on the day of study drug administration)

Grade 2 immune-related AEs should be managed as follows:

- If a Grade 2 ADR resolves to Grade  $\leq 1$  by the last day of the current cycle, treatment may continue.

- If a Grade 2 ADR does not resolve to Grade  $\leq 1$  by the last day of the current cycle, infusions should not be given on the following cycle. If at the end of the following cycle the event has not resolved to Grade 1, the subject should permanently discontinue treatment with avelumab ADR (except for hormone insufficiencies and conditions that are adequately treated with medical management, that can be managed by replacement therapy; for these hormone insufficiencies, up to 2 subsequent doses may be omitted). Patients with transient, minor Grade 2 ADRs, may be permitted to continue therapy with permission of the study PI provided the patient is adequately managed medically.

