- Upon the second occurrence of the same Grade 2 ADR (except for hormone insufficiencies that can be managed by replacement therapy) in the same subject, treatment with avelumab has to be permanently discontinued

There will be no dose modifications for avelumab in this study. Dose interruptions for reasons other than toxicity (e.g., surgical procedures) may be allowed with PI approval. The investigator and the PI will determine the acceptable length of treatment interruption. If avelumab is withheld for > 8 weeks then study treatment will be permanently discontinued.

If the investigator believes the patient is likely to derive clinical benefit, avelumab treatment can be resumed after being withheld for > 8 weeks. If a patient must be tapered off corticosteroids used to treat adverse events, study treatment may be withheld for > 8 weeks with PI approval.

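### As supplied, section 5.2 lists an unresolved fall in Karnofsky status to 40 or below as an exception to the Grade 3 stopping rule, so the condition reads backwards

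*Combined protocol and SAP*

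**What the plan says.** Section 5.2 opens its list with the stem "Avelumab will be discontinued in the patient if there is unacceptable toxicity defined as". Three outer bullets follow: treatment-related death, Grade 4 events (with a carve-out for isolated laboratory values), and "Any Grade 3 AE except for any of the following". Five sub-bullets hang from the third. The last begins "Change in Karnofsky Performance Status to" 40 or below and is qualified by failure to return to 50 or above within 14 days. A parenthesis adds that "infusions should not be given on the following cycle, if the Karnofsky Performance Status is" 40 or below on the day of dosing.

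The same section limits long holds: "If avelumab is withheld for > 8 weeks then study treatment will be permanently discontinued". The next paragraph then says that, where the investigator expects clinical benefit, "avelumab treatment can be resumed after being withheld for > 8 weeks".

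Sections 8.5 and 11.4 both end treatment for unacceptable toxicity. Section 5.2 is where that term is defined for the individual patient. No other section names a Karnofsky level as a reason to stop.

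**The concern.** An exception to a stopping rule should describe the milder case. This one describes the worse case: the man who has become severely disabled and has not recovered after two weeks. Taken as written, his Karnofsky decline is excluded from the Grade 3 trigger, and the bullet asks only for a hold. The man whose status recovers in time does not meet the exception at all.

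The wording makes sense as an item directly under the stem, that is, as a definition of unacceptable toxicity. It does not make sense as an exception.

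What is at stake is a mandatory patient-level safety rule. Performance status is recorded at every visit, so the rule is consulted each time a dose is due. Stage 2 would add two or three sites (section 11.9), whose staff would have to apply the text as it stands.

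**Working it through.** No sample size, error rate or event count is involved. The check is one of list logic, with some simple arithmetic on what the bullet covers.

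**The five exceptions side by side (section 5.2)**

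| Exception | What earns the exemption |
|---|---|
| 1. Flu-like symptoms or fever | Lasts at most 6 hours and is controlled |
| 2. "Grade 3 fatigue, local reactions, headache, nausea, emesis that resolves to Grade" 1 | Lasts at most 24 hours and resolves |
| 3. Isolated laboratory values | Unlikely to be related, no clinical correlate, resolve within 7 days or by the next visit |
| 4. Tumor flare | Confined to tumor sites |
| 5. Karnofsky 40 or below | Does **not** resolve to 50 or above within 14 days |

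The first four are transient, resolving or local. Only the fifth is defined by failure to resolve.

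**The logic as supplied.** Stop if there is a Grade 3 event and not (exception 1 or 2 or 3 or 4 or 5).
- Recovery to 50 or above by day 14: exception 5 is false, so there is no exemption.
- No recovery by day 14: exception 5 is true, so the Karnofsky change is exempt and only the hold applies to it.

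**The logic with the bullet one level out.** Stop if there is treatment-related death, or a non-exempt Grade 4 event, or a non-exempt Grade 3 event, or a Karnofsky fall to 40 or below without recovery by day 14.
- Recovery by day 14: the Karnofsky change alone does not stop treatment, and the parenthesis withholds doses due while he is at 40 or below.
- No recovery by day 14: treatment stops. This is the ordering one would expect.

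**Comparison within 5.2.** A Grade 2 immune-related reaction that is still unresolved at the end of the following cycle leads to permanent discontinuation, apart from stated exceptions such as hormone insufficiency. Under the literal reading, a persistent Karnofsky of 40 or below has no equivalent consequence of its own.

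**What the bullet covers**
- Entry requires Karnofsky 70 or higher (section 7.1) and the trigger is 40 or below, so the fall is at least 70 − 40 = 30 points. Appendix A describes a score of 40 as disabled.
- Dosing is every 2 weeks, or 14 days, so the window is 14/14 = 1 dosing interval. "Cycles will be 4 weeks long and thus include 2 doses of avelumab" (section 5.1), so it is also 14/28 = 0.5 of a cycle.
- The hold removes 1 dose if applied by dosing day, or 2 doses if applied to the whole following cycle. The parenthesis mentions both.

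**What still stops such a man**
1. A separate Grade 3 or 4 event outside the exceptions, including Grade 3 fatigue lasting more than 24 hours (5.2).
2. Disease progression (8.5). Clinical deterioration may count (8.11.3), but no Karnofsky threshold is set for it, and treatment beyond radiologic or PSA progression is permitted (section 1, Design; section 8 footnotes).
3. Intolerable side effects (section 1; 5.1), which are not tied to any Karnofsky level.
4. The 8-week limit, which the investigator may override (5.2).
5. Discretionary withdrawal, including for a change in condition or loss of benefit (8.8.1). Section 8.10.6 also foresees stopping for global deterioration.

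A man caught by none of the five, who recovers after day 14, may be re-dosed under the literal text. The documents give no rate of Karnofsky decline, no recovery time and no start point for the 8-week clock. Neither the number of such men nor the number of infusions they would receive can be calculated.

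**The case against.** The strongest objection is that the inversion rests on the indent of one bullet in text extracted from PDF. List levels are uneven elsewhere in that text, for example in the exclusion criteria (7.2), the synopsis inclusion criteria and the schedule footnotes in section 8. An outer bullet at the end of a sub-list could be absorbed into it and would look exactly like this. The wording also fits the outer level better. This stands: the source must be checked first, and if the bullet is already at the outer level there is nothing to correct. The two list levels inside 5.2 are otherwise regular, so the supplied text cannot simply be set aside.

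The second objection is about size. A reader might infer that a man at 40 or below goes on being infused, or that he is exempt from every mandatory stop. The documents support neither. The parenthesis withholds the dose whenever he is at 40 or below on the dosing day. The exception covers the Karnofsky change, not a separate Grade 3 or 4 event behind it, and the other routes to stopping remain open. Nor do the documents show that re-dosing a man who has recovered is unsafe. All of this stands and confines the point to a narrow gap. It does not make the condition read the right way round.

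**Conclusion.** The point holds in a limited form and should be corrected. On the supplied text, a persistent fall to Karnofsky 40 or below is not in itself a mandatory discontinuation criterion, and the exception is inverted relative to the other four. The remaining exposure is a man who does not reach 50 within 14 days, meets no other stopping rule, recovers later and is re-dosed. Its frequency is unknown.

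Confidence is moderate, because the conclusion assumes that the indent in the source matches the supplied text. It would be wrong to extend the point to the trial's statistical properties. Section 5.3 defines unacceptable toxicity for the trial-level rule separately, and the sample size and primary analysis do not depend on this bullet.

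**What to change.** Check the level of the Karnofsky bullet in the source document. If it is nested as supplied, move it out one level so that it becomes a stand-alone criterion under the stem, and keep the parenthetical dosing-day hold for the first 14 days.

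If an exception was intended, reword it so that it applies to a fall that does resolve to 50 or above within 14 days. This is the weaker repair: no section assigns an adverse event grade to a Karnofsky change, so a persistent decline would stop treatment only if it were recorded as a Grade 3 or higher event.

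The cost is one line in a protocol amendment, which needs IRB approval (12.7). Visits, analyses and sample size do not change. The downside of moving the bullet is that a few men who recover late would stop avelumab permanently when they could otherwise have been held and re-dosed.

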### 5.3 Trial Stopping Rules

If at any time after the first 12 subjects are enrolled, the observed proportion of unacceptable treatment-related toxicity exceeds 25% by at least one standard error, accrual will be immediately suspended to the trial. Unacceptable toxicity will be defined as grade 3 or higher treatment related adverse events. Each patient will be categorized according to their most severe toxicity using NCI CTC v4.0 or the most current version.

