## **9.6 Safety Oversight Committee (SOC)**

The Duke Cancer Institute SOC is responsible for annual data and safety monitoring of DUHS sponsor-investigator phase I and II, therapeutic interventional studies that do not have an independent Data Safety Monitoring Board (DSMB). The primary focus of the SOC is review of safety data, toxicities and new information that may affect subject safety or efficacy. Annual safety reviews includes but may not be limited to review of safety data, enrollment status, stopping rules if applicable, accrual, toxicities, reference literature, and interim analyses as provided by the sponsor-investigator. The SOC in concert with the DCI Monitoring Team oversees the conduct of DUHS cancer-related, sponsor-investigator therapeutic intervention and prevention intervention studies that do not have an external monitoring plan, ensuring subject safety and that the protocol is conducted, recorded and reported in accordance with the protocol, standing operating procedures (SOPs), Good Clinical Practice (GCP), and applicable regulatory requirements.

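### The only quantified trial-level toxicity rule cannot act before 12 men are enrolled and gives a treatment-related death no weight of its own, so an accrual pause can come later than the data already require

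*Combined protocol and SAP*

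**What the plan says.** Section 5.3 sets one trial-level rule. It applies when "at any time after the first 12 subjects are enrolled, the observed proportion of unacceptable treatment-related toxicity exceeds 25% by at least one standard error". On a breach, "accrual will be immediately suspended to the trial". The event is broad: "Unacceptable toxicity will be defined as grade 3 or higher treatment related adverse events". Each man counts once: "Each patient will be categorized according to their most severe toxicity". No event counts, standard-error formula or error rates are given.

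Section 5.2 lists "Any grade 5 treatment-related death" among the reasons for discontinuing avelumab in the individual patient. No section attaches a trial-level action to such a death.

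Other oversight in the protocol:

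- **5.11:** the PI-sponsor may end the study at any time.
- **9.3:** serious events reach the lead site within 24 hours and are passed on to the drug supplier. They go to the IRB if judged reportable, and to the FDA if possibly related and unexpected.
- **9.6:** the Safety Oversight Committee (SOC) is "responsible for annual data and safety monitoring".
- **10.1:** the PI tabulates adverse events continuously and may amend or close the study if Grade III or IV events are unexpectedly frequent. Independent monitoring starts after three men.
- **12.6:** refers to a monitoring plan held separately, which is not among the documents.

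**The concern.** A stopping rule is written in advance so that a pause does not depend on the judgement of the people running the trial. This one has two gaps.

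First, it is silent for 12 of the 18 stage 1 men. Section 11.9 plans 12 to 18 months of accrual per stage. At an even pace the twelfth man arrives after about 12/18 of that time, or 8 to 12 months. During this period the data can already guarantee a breach while the rule still lets men enter.

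Second, the gravest outcome carries no weight of its own. The 5.2 line on treatment-related death has no effect where it stands, because a man who has died cannot be taken off drug. In 5.3 a death is one event among all Grade 3 or higher events.

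A smaller matter adds to both: with the standard error undefined, two competent statisticians could disagree on whether accrual must stop.

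**Working it through.** **Inputs.** Start after 12 men, reference rate 25%, margin one standard error, one count per man (5.3); 18 men in stage 1, 44 for analysis, 49 in total (11.1). The plan gives no operating characteristics for the toxicity rule, so there is no figure to reproduce for it. The Simon design that supplies the sample sizes does reproduce: type I error 0.0495, power 0.881, early termination 0.774. The true toxicity rates below are assumptions.

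**1. Boundary at 12.** The trigger is the smallest k with k/n − 0.25 ≥ SE. The SE is either √(0.25 × 0.75/n) or √(p(1 − p)/n) with p = k/n.

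| k of 12 | Excess over 25% | SE at 25% | SE at observed rate | Trigger |
|---|---|---|---|---|
| 4 | 0.083 | 0.125 | 0.136 | no, under both |
| 5 | 0.167 | 0.125 | 0.142 | yes, under both |

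**2. Certainty before 12.** Five affected men among the first 11 leave at least five at 12, whatever happens to the twelfth. The fifth event can come as early as man 5, so at most 7 further men can enter before the rule acts.

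**3. Size.** Let T be the man at whom the fifth event occurs. Then P(T = t) = C(t − 1, 4) p⁵(1 − p)^(t − 5). The chance of a guaranteed breach before 12 is P(T ≤ 11). The expected number of extra men is the sum of (12 − t)P(T = t) over t = 5 to 11. Dividing by P(T ≤ 11) gives the mean when it happens.

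| Assumed true rate | P(T ≤ 11) | Extra men, overall | Extra men, when it happens |
|---|---|---|---|
| 25% | 0.115 | 0.29 | 2.51 |
| 40% | 0.467 | 1.42 | 3.04 |
| 50% | 0.726 | 2.58 | 3.55 |

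This assumes men enter one at a time, with each outcome known before the next entry.

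**4. Effect of acting at the fifth event.** With a first look at 12, the trials with five affected men among the first 12 are exactly those already suspended at that look. Only the timing changes. Over 44 men at a true 25%, the suspension probability is 0.397 (SE at 25%) or 0.359 (observed SE), with or without the earlier action.

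Section 5.3 could also be read as a first look at 13. With the SE at 25%, the boundary at 13 is still 5 and nothing changes. With the observed SE, 5/13 exceeds 25% by 0.1346 against an SE of 0.1349, so the boundary is 6. Acting at the fifth event then raises the probability from 34.1% to 35.9%.

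**5. Deaths.** From step 1, four affected men do not trigger. If all four died of treatment and no other man had a Grade 3 or higher related event, 5.3 would require nothing. At an assumed related-death rate of 5%, four or more deaths in 12 has probability 0.002, two or more 0.12 and one or more 0.46.

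**6. The two standard errors.** They differ by one event at 7 of the 33 sample sizes from 12 to 44:

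| n | 13 | 20 | 23 | 27 | 30 | 37 | 44 |
|---|---|---|---|---|---|---|---|
| SE at 25% | 5 | 7 | 8 | 9 | 10 | 12 | 14 |
| Observed SE | 6 | 8 | 9 | 10 | 11 | 13 | 15 |

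**The case against.** A reader might infer that the trial has no other safety stop and that several deaths would go unanswered. The documents do not support that. The PI-sponsor can end the study at any time, the PI reviews events continuously, serious events are reported within 24 hours, and further monitoring can be prompted by toxicity. The separate monitoring plan cited in 12.6 may say more. What these routes lack is a threshold or a mandatory action. Section 10.1 names Grades III and IV but not V, and SOC review is annual.

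A reader might also take 2.5 to 3.6 extra men as the expected cost. Those means apply only when five events come early. The overall expectation at a true 25% is 0.3 men, and nothing in the documents supports rates of 40% to 50%; section 3.3.2 reports 1738 patients already treated at this dose. Known outcomes at each entry is also an optimistic assumption, since 5.10 and 8.6.2 recognise delayed immune toxicity. Later reporting would reduce the number of men spared. These points stand.

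A minimum sample before a proportion rule operates, and pooling Grades 3 to 5, are ordinary design choices. That is fair, but a minimum sample protects against an unstable proportion, and that reason is gone once the breach at 12 cannot be undone. Four deaths in 12 is an extreme case; the practical gap is the first or second related death, which also has no mandatory consequence.

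**Conclusion.** The concern holds in limited form. Section 5.3 is the only quantified trial-level toxicity rule in the documents, and it can delay a suspension that is already certain. The delay is small if true toxicity is near 25% (11% chance, 0.3 men on average) and material if it is much higher (73% and 2.6 men at 50%). Certainty at five events rests on a first look at 12 men, or on a first look at 13 with the standard error taken at 25%.

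Separately, a treatment-related death has no mandatory trial-level consequence. Up to four in 12 men fit under the boundary, provided no other man has a Grade 3 or higher related event. The undefined standard error is a minor defect: one event, at a minority of sample sizes.

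The plan should be changed, because the changes are specific and cheap. The finding is not that safety oversight is absent.

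**What to change.** All three changes concern when accrual pauses. They leave the treatment of men already on study untouched.

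1. State in 5.3 that accrual is suspended as soon as five of the first 12 treated men have had a Grade 3 or higher related event, even if fewer than 12 are enrolled. From 12 men on, the boundary for the current number treated applies. The limit to the first 12 is essential: if a fifth event at any sample size suspended accrual, the chance over 44 men at a true 25% would be 99%, against 36% to 40% now. With a first look at 12, the overall suspension probability does not change. With a first look at 13 and the observed SE, it rises from 34.1% to 35.9% at a true 25%.
2. Reconcile the Grade 5 line in 5.2 with 5.3 by making a treatment-related death a trial-level trigger that pauses accrual pending an ad hoc SOC review. The cost is a possible short pause. At an assumed related-death rate of 1%, the chance of at least one is 11% in the first 12 men and 39% over 49 (1 − 0.99⁴⁹).
3. Replace the formula with a printed table of counts by number treated, using one stated standard error, and say whether the first look is at 12 or 13. This costs only wording.
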